#### Exclusion Criteria:

1. Participant child is experiencing severe self-injurious behavior or severe aggressive behavior to self or others (within past 7 days).
2. Participant has been diagnosed with another psychiatric or neurological disorder (e.g. epilepsy) or have exhibited symptoms of major psychiatric disorders within the last 30 days.
3. Participant has an unstable medical condition (that requires clinical attention).
4. Participant has a significant skin condition at the procedure sites (i.e., hemangioma, scleroderma, psoriasis, rash, open wound or tattoo).
5. Participant has an implant of any kind in the head (e.g. stent, clipped aneurysm, embolised AVM, implantable shunt - Hakim valve).
6. Any use of light-activated drugs (photodynamic therapy) within 14 days prior to study enrollment (in US: Visudine (verteporfin) - for age related macular degeneration; Aminolevulinic Acid- for actinic keratoses; Photofrin (porfimer sodium) - for esophageal cancer, non-small cell lung cancer; Levulan Kerastick (aminolevulinic acid HCl) - for actinic keratosis; 5-aminolevulinic acid (ALA)- for non-melanoma skin cancer).
7. Current treatment with a psychotropic medication.
8. Investigator and his/her immediate family, defined as the investigator's child or grandchild.

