**7.0 Procedures Involved:**

7.1 Location: The study will use pre-test and post-test design. The entire study on the children will be done in the office. The weekly interview with the parent may be done either in office or by phone, as preferred by the parent.

7.2 Conditions: There will be only one active condition.

7.3 Participants: The participants will be 2 to 7 years old children previously diagnosed with moderate or severe ASD. Children of all genders and races will be included in this study.

7.4 Treatment: The treatment will take place twice a week for up to 30 minutes at a time.

During the study, while participants will be wearing the photobiomodulation device, they may be playing with their parent or the experimenter, using the toys of their choice (out of the many available in the experimenter's office). The caregivers will be present during the experiment at all times. When the child and the parent arrive, they will be welcomed to the office, and introduced to the toys.

The child will be encouraged to play with toys and interact with the parent (or the experimenter).

If the child becomes uncomfortable, the parents will be able to leave the experiment without any punishment. No coercion or deception is involved in this study.

7.5 Pre and Post-Testing:

The following measurements will be used for pretest and post-test.

- Childhood Autism Rating Scale (CARS2)

CARS 2 scores will be compared for analyses.

In addition, EEG will be collected from the participants pre and post -treatment in each session. Mobile FDA cleared EEG device from Brain Scientific will be used to collect children's pre and post test EEG.

There is no known danger of EEG collecting. In this study it will be using for measuring the efficacy treatment only.

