**7.6 On-going Data Collection:** Parents will be asked to keep a daily diary of the child's behavior, specifically – words spoken, comprehension of instructions, eye contact, his sleep pattern, number of tantrums, anxiety, social interaction and eating. Qualitative data will be collected through short weekly interviews with the parents. These interviews can take place either in [name] office during the child's treatment or by phone. During those weekly interviews, the parents will be asked questions about their children's responsiveness to language, number of words they can produce, eye-contact, anxiety, frequency of tantrums, eating, and difficulties falling asleep and sleeping through the night. Please see attached proposed script for the weekly call. The qualitative data will be used to further inform and supplement quantitative data.

The study will collect qualitative and quantitative data. The quantitative data will be the total CARS2 scores of the participants, obtained before and after the study is done. Repeated-measure t-tests will be used to analyze quantitative data. In addition, we will collect Before and After Prefrontal cortex EEG from the control and experimental treatment groups to measure electrophysiological changes in Prefrontal cortex. after treatment. EEG data will be analyzed (using Time-Frequency analysis), and after baseline normalization, the data will be used in aggregate to compare conditions numerically. In addition, we will obtain qualitative data from weekly parental interviews, during which we will ask participants' parents about their children's behavior (see attached protocol). Qualitative data will be used for information purposes and will supplement quantitative data.

The PI will analyze quantitative and qualitative data. An independent contractor (a neuroscientist) will be analyzing the collected EEG data at the end of the study, however, the individuals conducting the analysis will not have access to the private identifiable information.

**7.8 Confidentiality:** Participants' confidentiality will be protected by assigning them Study ID. The quantitative data will be analyzed and reported only as aggregate (averages and F scores). The qualitative data will be studied only by the researchers and, if reported for illustrative purposes only, it will be attached to the Study ID (not the identifying information). The participants will be asked for consent to report qualitative data with the Study ID.

●

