## 8.0 Recruitment Methods:

We will contact via phone call the parents of children who have participated in our previous study, approved by the WCG IRB under IRB Tracking ID 120200004.

Once a prospective parent contacts the researchers, they will be re-screened for eligibility. They will be asked questions regarding the Inclusion and Exclusion criteria. If the child is determined eligible, we will schedule their first session, which will start with debriefing about the purposes of the study, benefits and risks. After debriefing, participants will sign the Informed Consent (if they are still willing to

participate), and proceed to the study. (Please see attached script for eligibility screening and obtaining Informed Consent).

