#### 15.0 Data Monitoring Plan to Ensure the Safety of Participants:

We will conduct weekly interviews with the parents, asking them questions about child's behavior and functioning to collect both safety and efficacy data. The interviews will be conducted either by telephone or in person (per parental choice). Please attached interview protocol. [name], a licensed clinical psychologist will review the data. The detailed qualitative data will be collected. No statistical analysis is necessary.

If a participant shows sudden developmental regress, we will recommend immediate neurological evaluation and his/her participation will be discontinued (unless this participant has been manifesting regress prior the start of the study). If two participants suddenly manifest signs of regress (not anticipated, not seen before in prior photobiomodulation studies), we will immediately discontinue the study.

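### Safety is asked about once a week while the device is used twice a week, so at least half of sessions start with no scheduled safety question since the previous session

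*Protocol*

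**What the plan says.** Section 15.0 of the protocol names the safety data source: "We will conduct weekly interviews with the parents, asking them questions about child's behavior and functioning to collect both safety and efficacy data". A licensed psychologist reviews these data, with no interval stated. The same section gives two rules that depend on them. For one child: "If a participant shows sudden developmental regress, we will recommend immediate neurological evaluation and his/her participation will be discontinued", with an exception for a child who was already regressing before the study began. For the study as a whole, unexpected regress in two children ends it.

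Section 7.4 gives the treatment frequency: "The treatment will take place twice a week for up to 30 minutes at a time". Section 7.6 says the interviews can be held in the office "during the child's treatment or by phone". Its topics are language, eye contact, anxiety, tantrums, eating and sleep.

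Three other arrangements bear on the point. Section 7.4 says: "The caregivers will be present during the experiment at all times". Section 7.6 has parents keep a daily behaviour diary. Section 13.0 has clinicians follow each child's progress through interviews with parents and therapists.

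On eligibility, section 8.0 describes a re-screen by questions to the parent and continues: "If the child is determined eligible, we will schedule their first session". That session is described as debriefing, consent and then the study. Section 5.0, by contrast, treats screening as already finished.

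The SAP text supplied deals with CARS scores and says nothing about collecting safety data.

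**The concern.** Tolerability and safety are among the purposes listed in section 1.0. The one scheduled safety enquiry runs at half the frequency of exposure, and its timing relative to sessions is left open. A parent may have noticed something that section 15.0 would act on, yet the next session can begin before anyone is due to ask. The two-child rule draws on the same flow, so late detection in one child can also delay a decision that affects every enrolled child.

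A second loss concerns the data. Section 13.0 lists headaches, agitation and hyperactivity as possible transient effects, sometimes seen early in treatment. None is among the interview topics in section 7.6, although anxiety and tantrums overlap with agitation. Anything a parent does mention is recalled over as much as a week and is not tied to a session. The study could then report that effects were or were not mentioned, but not how often they followed a session or whether they faded. Section 10.0 notes the children's limited comprehension, so the parent is the practical source.

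**Working it through.** The documents give no figure for safety detection, so there is none to reproduce. The check is a count of the schedule.

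**Inputs.** Sessions: 2 per week (section 7.4). Interviews: 1 per week (sections 7.6 and 15.0). Course: 10 weeks (section 1.0) or 12 weeks (the restart provision in section 13.0). The two lengths must be reconciled, and both are shown.

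**Sessions with no enquiry since the previous one.** An interview falls in at most one gap between sessions, so the minimum number of sessions without one is sessions minus interviews.
- 10 weeks: 2 × 10 − 10 = 10 of 20 (50%).
- 12 weeks: 2 × 12 − 12 = 12 of 24 (50%).

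This is the most favourable placement. If every interview is held with the device on, no session is preceded by an enquiry made after the previous session ended.

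**Sessions between a sign and the next interview.** Two sessions fall in each weekly interval, so a sign just after an interview can be followed by two: 2/20 = 10% of a 10-week course, or 2/24 = 8% of a 12-week course. This is the regular timetable. Section 13.0 lets a cancelled session be made up within 7 days, which could add to it.

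**How often, under assumptions.** Assume the week's second session is g days after its first (g = 2 to 4; spacing is not stated) and that a sign starts at a uniformly random time in the 7-day cycle.
- Interview just before the first session: P(at least one session starts before the next interview) = g/7, from 2/7 = 29% to 4/7 = 57%.
- Interview during the first session: at least one session always starts first. P(two) = g/7 = 29% to 57%, and the mean is (7 + g)/7 = 1.3 to 1.6 sessions.

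**With a question before every session.** Sessions starting without an enquiry since the previous one fall from at least 10 of 20 to 0 of 20.

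**Eligibility windows (secondary).** The days of a look-back window that fall after the re-screen are min(lag, window). The lag from re-screen to first session is not given, so the values below are assumptions.

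| Assumed lag | 7-day window | 14-day window | 30-day window |
|---|---|---|---|
| 3 days | 3 of 7 | 3 of 14 | 3 of 30 |
| 7 days | 7 of 7 | 7 of 14 | 7 of 30 |
| 14 days | 7 of 7 | 14 of 14 | 14 of 30 |
| 30 days | 7 of 7 | 14 of 14 | 30 of 30 |

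Only the 14-day exclusion has a stated reference point (enrolment). Consent is signed at the first session.

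**The case against.** The strongest reply is that the weekly interview is not the only way regress could reach the study. Parents keep a daily diary covering areas where regress would show. A caregiver attends every session, staff see the child twice a week, and clinicians follow progress. This stands, and it rules out saying that the study has no other route to the information. What remains is that no supplied passage says when the diary is read or makes a question before each session a step, and the list of study data in section 14.0 does not include the diary.

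A reader might infer that weekly enquiry contradicts section 15.0's use of the word immediate. It does not. The word describes the recommendation made once regress is shown, and it sets no detection interval.

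A reader might also take section 7.6 to mean that parents are always questioned with the device already on. The wording permits that, but treatment there may mean the whole appointment, and a phone call is the alternative.

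On eligibility, a reader might conclude that time-limited exclusions are settled by phone and have lapsed by the first session. Section 8.0 makes first contact by phone but does not state how the re-screen is done, and it gives no interval. It also refers to an attached script that was not supplied. The interview script is likewise missing from the material, so either attachment may already contain the check.

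Finally, section 3.0 reports a non-significant-risk designation for the device, and no efficacy estimate is affected. Both are true, and they limit the weight of the point.

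**Conclusion.** The point holds as a low-cost improvement to safety data collection. It is not an internal contradiction or a flaw in the CARS analysis. From the stated frequencies alone, at least half of sessions start with no scheduled safety enquiry since the previous one, and up to two can start between a sign of regress and the next interview. These counts need only the regular timetable. The 29% to 57% range also needs the assumed session spacing and onset at a random time.

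Transient effects named in section 13.0 are absent from the listed interview topics, so tolerability is not captured by session in the text supplied. The actual gap will be smaller if staff routinely talk to parents or read the diary, and it may be closed by an attachment not available here.

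The eligibility part is a request for clarification. Sections 5.0 and 8.0 disagree on whether screening is finished, and the unseen share of each window depends on a lag that the protocol does not give.

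**What to change.** At each visit, when the pre-treatment EEG described in section 7.5 is taken, ask the attending parent a short fixed set of questions on regress and side effects, including the effects named in section 13.0. Look at the diary at the same time, and record the answers against the session number. Add the diary and this form to the data list in section 14.0. Keep the weekly interview for its behavioural topics. The discontinuation rules in section 15.0 stay as they are; only the timing and recording of the enquiry change.

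The cost is one form and about a minute per visit: 20 × 1 = 20 minutes per child over 10 weeks, and 30 × 20 = 600 minutes (10 hours) for 30 children. Over 12 weeks it is 24 minutes per child and 12 hours in all. Asking more often will probably bring more reports, so give results per session as well as per child.

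As a secondary clarification, reconcile sections 5.0 and 8.0 on screening, and sections 1.0 and 13.0 on course length. Confirm the 7-, 14- and 30-day exclusions at the consent visit, unless the attached script already does so. If either attachment already contains these checks, a cross-reference is enough for that part.

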# **Transcranial Photobiomodulation for reducing autism symptoms in children.**

*May 1, 2022*

PROTOCOL TITLE:

Transcranial photobiomodulation for reducing autism symptoms in children.

PRINCIPAL INVESTIGATOR:

Name	[name]
Department	N/A
[contact]

RESEARCHERS:

Name	[name]
Department	N/A
[contact]

Name	[name], CFA, Esq.
Department	N/A
[contact]

Name	[name]
Department	N/A
[contact]

1.0 Purpose of the study:

The purpose of this 10-week feasibility study is to assess the tolerability, safety and efficacy of Transcranial LED Therapy for language learning and reducing symptoms of autism in children.

The investigators propose to enroll up to 30 participants, 2-7 years old, all of whom have recently completed the IRB approved study by JelikaLIt. They all have been previously diagnosed with moderate to severe ASD by licensed professionals according to the Diagnostic and Statistical Manual of Mental Disorders, Fifth Edition (DSM-5) criteria for Autism Spectrum Disorder (ASD).

This will be an one-arm, open label study. Participants who were in the placebo condition in the previous study, will receive the treatment. Participants who were in the active condition in the previous study will repeat the course of treatment after the intermission of 3-6 months (depending on when they completed the study).

The hypothesis to be tested is that exposure to photobiomodulation will reduce children's symptoms of autism, as measured by the reduction of the Mean Scores of the Childhood Autism Rating Scales, compared to the initial baseline.

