## 2.3 Background of the Cognilum Physical Device:

We are developing a safe and effective protocol for administering tPBM via a wearable device. This physical device is getting developed by JelikaLite Corp. The parameters are developed by [name] (the researcher of this study), [name] (leading photobiomodulation expert from Harvard Medical School and an advisor to JelikaLite), [name] (leading neuroscientist who is studying photobiomodulation at Boston Medical University and an advisor to JelikaLite), and [name] (an industrial product designer with over 30 years of expertise in designing medical devices). The purpose of this feasibility study is to evaluate the safety and comfort of the product, as well as preliminary efficacy of the treatment effect. The device will stimulate Default Mode Network (to increase brain connectiveness) as well as Broca and Wernike areas (to facilitate speech comprehension and production) and Occipital lobe (as many ASD children rely on visual information for language learning). The device is physically light, comfortable to wear for children and could eventually be used at home as frequently as necessary.

The reason why the device may be helpful to children is because of the science of photobiomodulation. The device will have embedded LED lights in it, which will shine red light and near infra red lights. The children will wear the device for approximately 5-10 minutes, twice a week (closely replicating the protocol of Leisman et al as well as the clinical study at MGH). The light stimulates mitochondrial ATP production. Only about 2% of the light penetrates the skull. However, because brain is the largest energy consuming organ of the body, even those 2% result in significant improvement of the symptoms (even small boost in ATP production results in significant improvement). Having more energy enables the brain cells to heal, grow and form new neural connections. Other benefits of tPBM is increased blood flow to the brain, which increase brain oxygen supply and reduce inflammation.

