Some participants may have to be withdrawn from the study	If the child is not able to attend all the required sessions and the caregiver is not able to reschedule a cancelled session within a 7-day window, then the child may have to be withdrawn from the study.

	
 
1. If the child has completed at least 8 weeks, we will ask them to do final assessments and this data will be included in the final analysis.
 
2. If the child has completed less than 8 weeks and missed a week due to sickness, the family will be offered to restart the 12-week course. Regardless of the outcome, we will ask the child's parents for permission to contact them in the future with follow up questions regarding the child's behavior.
 

--	-------------------------------------------------------------------------------------------------------------------------------------------------------------------------------------------------------------------------------------------------------------------------------------------------------------------------------------------------------------------------------------------------------------------------------------------------------------------------------------------------------------------------

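### The stopping rule in section 15.0 exempts a child by history of regress alone, so read literally it removes the mandatory stop after a new sudden loss

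*Protocol*

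**What the plan says.** Protocol section 15.0 sets two stopping rules for harm.

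- **One child.** If a child suddenly regresses, "we will recommend immediate neurological evaluation" and "his/her participation will be discontinued (unless this participant has been manifesting regress prior the start of the study".
- **The study.** "If two participants suddenly manifest signs of regress (not anticipated, not seen before in prior photobiomodulation studies), we will immediately discontinue the study".

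A licensed clinical psychologist reviews the weekly parent interviews, and the section states that no statistical analysis is needed. The treatment to which the rules apply is described in section 1.0 ("The purpose of this 10-week feasibility study is to assess the tolerability, safety and efficacy") and section 7.4 ("The treatment will take place twice a week for up to 30 minutes at a time"). Section 1.0 also says that children who were in the active arm of the sponsor's earlier trial repeat the course after a break of 3 to 6 months.

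**The concern.** The first rule responds to a sudden loss during treatment. Its exception asks a different question, namely whether the child had been regressing before the study. It does not ask whether the new loss is faster than before, affects another skill, or comes after a stable period. A child could therefore have the event the rule was written for and still fall outside the mandatory stop.

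The date used in the exception adds to this. All children come from the earlier trial, so the period before this study includes the former active arm's first exposure to the device. A regress that began after that exposure would count as prior history and would qualify the child for the exception. The documents report no such case, but the wording does not exclude one.

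The children are 2 to 7 years old, and section 10.0 accepts that they may be unable to give verbal assent. A stop made by the investigators therefore carries real weight, and its wording should be settled before the first session.

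**Working it through.** No operating characteristic is stated for these rules and no regress rate is given, so there is no figure of the plan's to reproduce. The check is a reading of the text, followed by the little arithmetic that applies.

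**1. What the exception attaches to.** On the natural reading it qualifies discontinuation only. The recommendation of a neurological evaluation comes before it and appears to stand for every child.

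**2. Outcome by type of child with a sudden loss on study.**

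| History at entry | Event on study | Literal reading | Narrow reading (ongoing decline only) |
|---|---|---|---|
| No regress | Sudden loss | Discontinued | Discontinued |
| Declining | Same course continues | Exempt | Exempt |
| Declining | New or faster loss | Exempt | Not clearly exempt |
| Earlier regress, since stable | New sudden loss | Exempt | Discontinued |

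The readings part in the last two rows. An unchanged, known decline would seldom be called sudden, so the exception matters most in those rows.

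**3. Whether another section closes the gap.**
- Section 4.0: no criterion names regress. Exclusion 3 (unstable medical condition) may keep out some children in active decline.
- Section 8.0: re-screening covers the inclusion and exclusion criteria. It is not said to record whether a child is declining.
- Withdrawal from the Study: this covers withdrawal by the family's choice.
- Section 13.0: this deals with discomfort from the headband and with missed sessions. It says that clinicians will monitor progress but sets no stop.
- Section 7.5: EEG is described as a measure of efficacy only.
- SAP: it reports CARS analyses and contains no safety rule.

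None of these limits the exception. The screening script and the interview protocol are attachments that I could not see, and neither was the text between sections 5.0 and 7.0. They may address the point.

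**4. The two-child rule.** Its sentence refers to any two participants and carries no exception for history. On its words, an exempt child counts if the signs are sudden and unanticipated. The only doubt is whether someone could call a new loss *anticipated* because the child had regressed before.

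**5. Arithmetic.**
- Full course: 10 weeks × 2 = 20 sessions, at most 20 × 30 min = 10 hours. Section 2.3 gives a shorter session ("The children will wear the device for approximately 5-10 minutes, twice a week"), and then 20 × 5 to 10 min = 100 to 200 minutes.
- Sessions left after a loss at the end of week w: 2 × (10 − w). For illustration, w = 2, 5 and 8 leave 16, 10 and 4 sessions. This bounds the exposure left in place. It does not measure harm.
- Two-week hold: 2 × 2 = 4 sessions, and 4/20 = 20% of the course. Section 13.0 also mentions a 12-week course ("the family will be offered to restart the 12-week course"), and then 4/24 = 17%.

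**The case against.** The strongest reply is that the narrow reading is the better one. The clause describes a process already under way at entry, and beside a trigger of *sudden* regress it may say only that a known decline is not a trigger. That reading is reasonable, but the text does not impose it, and two careful investigators could treat the same child differently.

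Second, protections remain. Staying on treatment is permitted and not required, evaluation still appears to be recommended, a psychologist reviews the data each week, and the family may leave at any time. This stands and lowers the risk, but none of it is a stop.

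Third, a prior trend could be reconstructed. The SAP reports CARS ratings before and after the earlier trial, with none missing among completers, and section 7.5 adds a new pre-test CARS2. This is fair: the information partly exists. The protocol does not say that it will be used to apply the exception.

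Fourth, no affected child is shown. The cohort is closed, has at most 30 children and is known to the investigators. This also stands.

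A reader might infer that the study stop leaves these children out as well. The documents do not support that, because the exception sits in the sentence on the individual child and is not repeated in the two-child rule.

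**Conclusion.** The point holds as a minor correction to a safety rule. Section 15.0 ties the exception to history and does not require that the event on study be only a continuation. Read literally, it removes the mandatory stop for a child with earlier regress who has a new sudden loss, and it does so even if the earlier regress followed device exposure in the first trial.

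Three stronger conclusions might be drawn, and the documents do not carry them. They do not show that any child would in fact be kept on the device after a new loss. The number of sessions remaining is not an estimate of harm. No probability of a missed stop can be given, because the number of children with earlier regress is not stated and may be zero.

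The conclusion assumes that the attachments and the text I could not see do not already narrow the exception.

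**What to change.** Change section 15.0 in three places.

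1. Limit the exception to the unchanged continuation of a decline recorded at re-screening, before the first session. The topics already asked in the weekly interviews can serve as the entry questions.
2. For any new or faster sudden loss, whatever the history, hold treatment until the recommended neurological evaluation is done. Children without earlier regress continue to be discontinued as now. State that the hold falls outside the rescheduling rule in section 13.0, under which a family "not able to reschedule a cancelled session within a 7-day window, then the child may have to be withdrawn". Otherwise a hold of more than a week could end as a withdrawal for missed sessions.
3. Add one clause to the two-child rule: earlier regress does not by itself make a new sudden loss anticipated.

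Leave the judgement of what is a sudden regress to the reviewing psychologist. I would not add a numerical trigger based on weekly parent reports. With up to 30 × 10 = 300 child-weeks, suppose that natural fluctuation produces a confirmed event at a rate r per child-week, independently. The chance per child is p = 1 − (1 − r)^10, and the chance that two or more of 30 children trigger a stop is 1 − (1 − p)^30 − 30p(1 − p)^29. For assumed rates of 0.1%, 0.5% and 1% this is about 4%, 43% and 80%. The documents give no rate, so such a threshold could stop the study for natural course alone.

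The cost is two or three sentences and a few entry questions, with no extra study visits. Some holds will be for natural course, and a two-week hold takes 4 of an affected child's 20 sessions.
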